During the study period, subjects will have visits every two to three months, i.e., at months 2, 4, 6, 8, 10, 12, 15, 18, 21 and 24. During these visits, plasma oxalate and safety labs will be taken. Subjects will be asked to provide stool samples four times (months 6, 12, 18 and 24) and 24-hour urine five times (months 4, 8, 12, 18 and 24). In addition, subjects will provide a post-treatment follow-up stool sample 4 weeks after intake of last dose of study drug. Echocardiography (STE and traditional) will be assessed four times (months 6, 12, 18 and 24). Ultrasound of the kidney will be done two times (months 12 and 24). Quality of Life will be evaluated by a questionnaire during months

6, 12, 18 and 24 (Table 5). Information on kidney stone events and related symptoms will be captured throughout the study.

Adverse events and concomitant medication will be monitored throughout the study.

Safety evaluation will include physical examination, vital signs and safety labs. Monitoring of AEs, concomitant medication and compliance with the administration of study drug will be performed at each visit. In addition, there will be a 4-week safety follow-up after intake of the last dose of study drug. Furthermore, questions on kidney stone events and related symptoms will also be asked throughout the study.

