7.4 Subject Withdrawal Criteria

If a subject fails to return for a scheduled study visit, the investigator will make a reasonable effort to contact the subject and determine why the subject failed to return and to schedule a new study visit. Any information obtained during this contact will be documented in the study records.

A study subject will be discontinued from treatment in the study if:

- Any clinically significant AE, laboratory abnormality, illness, or other medical condition or situation occurs such that continued participation in the study would not be in the best interest of the subject.
- OxThera or the Principal Investigator in consultation with OxThera may discontinue the subject at any time for medical and/or administrative reasons.
- The Prinicpal Investigator in consultation with OxThera may discontinue the subject in case of a major protocol violation.
- The subject requires dialysis.

Protocol OC5-OL-02, Confidential

Any subject who withdraws prematurely from the study treatment will be asked to complete all study assessments scheduled for the month 12 or 24 visit at the time of withdrawal and will be followed for safety for 4 weeks after the last intake of study drug. Subjects will provide a stool sample 4 weeks after end of treatment.

Patients who withdraw consent from participating in the study at any time will end the study. They will not have any further assessment and no further study data will be collected.

For any subject who has withdrawn, the date of withdrawal from the study and the reason for withdrawal from treatment and from the study will be recorded in the source data and eCRF.

Withdrawn subjects will not be re-entered into the study.

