3 PATIENTS FOR ANALYSIS

3.1 Analysis populations

3.1.1 Full-Analysis-Set (FAS)

The FAS includes all subjects who have received at least one dose of the investigational drug during the ePHex-OLE study and have at least one efficacy assessment during the ePHex-OLE study. This population will be used for the analysis of efficacy.

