7.6.2 Key secondary endpoints

The key secondary endpoints will be presented using the FAS population, and all individual data will be listed as well.

Total plasma oxalate

The key secondary endpoint change from baseline in total plasma oxalate concentration, will be analysed using a similar analysis (descriptive plus supportive MRMM including the slopes) as proposed for the primary endpoint (see section 7.6.1), and no additional sensitivity analyses will be performed. Similar descriptive statistics per visit (absolute and change from baseline) and plots will be created.

Additionally, a combined plot for total plasma oxalate concentration and eGFR over time will be created using a double-axis display – this plot will be created for each subject, and a summary plot presenting mean +/- SE values per treatment group and overall will be made.

Summary statistics will also be created for the observed minimum and maximum total plasma oxalate concentration values during ePHex-OLE, as well as its changes from baseline using both baselines. Also, plots will be created to present the shift from baseline to the minimum or maximum value, combined for all subjects per treatment group and overall.

In addition, a frequency tabulation will be created based on the number of subjects achieving ‘near-normalization’ of total plasma oxalate concentration (<10 µmol/L) at least twice during 12 months and during 24 months of open-label treatment. This table will also include the response assessments for < 10 µmol/L during 12 months and during 24 months of open-label treatment.

Furthermore, percent change from baseline in total plasma oxalate concentration after 12 and 24 months of treatment will be displayed descriptively per treatment and overall, using both baselines.

Kidney stone events

Kidney stone events are defined as subject- or investigator reported symptoms (as in the CRF AE or PH medical history pages), or number of stones assessed by Ultrasound (US). As a consequence, three summary tables on stone events will be presented, as follows:

- Stone events during treatment, based on AE
- Stone events during treatment, based on US

Here, during treatment is defined as first to last dose date of ePHex-OLE. Where applicable, stones left and right will be combined into one overall kidney stone number for summary tables and analysis.

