Descriptive statistics of the occurrence of kidney stones and the number of subjects with a stone event after 12 and 24 months of open label treatment will be presented per treatment group and overall, separately as based on AE and based on US datasets.

Descriptive statistics on stone events using the AE dataset will include a summary of days missed at school/work due to a stone event and other relevant data related to stone events.

Incidence rate of kidney stones is the rate at which kidney stone events occur in the population, and defined as the number of kidney stone cases per subject-year(s). The calculation of the incidence rate is the number of kidney stone occurrences during the study time period divided by the group of subjects susceptible to a stone event (i.e. the FAS), expressed as person-time and

calculated as sum of the treatment duration time of all subjects in the FAS. This calculation is accomplished as follows:

- Denominator: $\sum t_i$, where t_i = treatment duration of subject i in years (total # days divided by 365.25), where treatment duration is determined based on first and last dose date.
- Numerator: the total number of kidney stone occurrences during treatment (first to last dose date)
- Incidence rate=numerator/denominator

Since this analysis is done both after 12 months and after 24 months of treatment, in case of 12 months the date of visit 6 is used instead of last dose date.

The use of this measure implies the assumption that the incidence rate is constant of different periods of time. The incidence rates will be presented per treatment group. As these incidence rates are determined per treatment group, comparisons can be done using descriptive statistics of incidence rate difference (IRD) and incidence rate ratios (IRR). IRD and IRR are defined as follows, assuming the following exposure table:

			Treatment exposure	
			O - O	P - O
Outcome	12 months	Occurrences	a	B
		Person-time	PT1	PT2
	24 months	Occurrences	a	b
		Person-time	PT1	PT2

Then $IRD=(a/PT1) - (b/PT2)$ and $IRR=(a/PT1)/(b/PT2)$ is calculated for 12 months and 24 months. These will be presented in combination with a 95% CI.

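### SAP 7.6.2 can exclude closing ultrasound scans from the stone count while keeping their treatment time, and it leaves the 12-month window undefined for subjects without a Visit 6

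*SAP*

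**What the plan says.** Kidney stone frequency after 12 and 24 months is a key secondary endpoint (SAP 6.2). SAP 7.6.2 summarises it separately from adverse event records and from ultrasound, and one window serves both: "Here, during treatment is defined as first to last dose date of ePHex-OLE".

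The incidence rate is events divided by person-time. Person-time is "calculated as sum of the treatment duration time of all subjects in the FAS", "where treatment duration is determined based on first and last dose date", and the numerator is bounded by the same two dates. For the 12-month version the SAP adds that "in case of 12 months the date of visit 6 is used instead of last dose date". Rate differences and rate ratios between O-O and P-O follow, with 95% confidence intervals. The table list in SAP 12.3 (14.2.30 and 14.2.33) confirms that rates and any count model are produced on ultrasound data as well as adverse event data.

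Three other provisions matter:

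- The on-treatment renal ultrasounds are scheduled at Months 12 and 24 only (Protocol 6.2).
- A subject who stops treatment early is asked to "complete all study assessments scheduled for the month 12 or 24 visit at the time of withdrawal" (Protocol 7.4).
- Entry to the FAS needs one dose and that the subject "have at least one efficacy assessment during the ePHex-OLE study" (SAP 3.1.1). Reaching Visit 6 is not required.

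**The concern.** **Ultrasound.** A symptomatic event has its own date. A stone found by imaging has only the date of the scan that showed it. The withdrawal scan is requested from someone who has already stopped, or is stopping, treatment, so a scan date after the last dose is the natural sequence. For a subject who leaves before Month 12 it is the only follow-up scan. Under the literal window its findings do not count, yet the months on treatment that produced them remain in the 24-month denominator. The same happens to a Month 24 scan done after the last capsule. No sentence in SAP 7.6.2 assigns such a scan to the treatment period.

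**12-month window.** The last dose date is replaced by the Visit 6 date, with no fallback for a subject who has none. Such a subject is still in the FAS, so the requirement to sum over all FAS subjects cannot be met as written. SAP 7.2 imputes nothing unless specified, so a missing duration is the likely programmed result. If ePHex-OLE closes early, SAP 7.1 (option 2) still reports the key secondary endpoints, and more subjects could then lack a Visit 6.

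At stake are the reported rates, rate differences and rate ratios. The ratio is distorted if the two groups lose subjects unequally.

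**Working it through.** **Inputs.** 16 entrants, 25% drop-out per year, about 12 and 9 completers (Protocol 12.2, SAP 2.4); 18 subjects actually included (SAP 2.4). Neither document gives exit times or a planned stone rate. I assume a constant event rate and that leavers spend on average *m* = 0.5 year on treatment in the year they leave, with a range of 0.25 to 0.75.

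**Step 1: the plan's own figures.** 16 × 0.75 = 12 and 16 × 0.75² = 9, as stated. So 4 leave in year 1 and 3 in year 2.

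**Step 2: ultrasound rate over 24 months.**

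- Person-years: 9 × 2 + 3 × (1 + *m*) + 4 × *m*. At *m* = 0.5: 18 + 4.5 + 2 = 24.5.
- Leavers' time since their last scheduled scan, visible only on the closing scan: (3 + 4) × 0.5 = 3.5.
- Share affected: 3.5 / 24.5 = 14%. If all those scans fall after the last dose, the rate is 21 / 24.5 = 0.86 of its true value.
- Extreme case, with all 9 completers' Month 24 scans also after the last dose: (3.5 + 9) / 24.5 = 12.5 / 24.5 = 51%.

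**Step 3: 12-month rate.**

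- Full person-years: 12 × 1 + 4 × 0.5 = 14.0. Without the leavers: 12.0. Lost: 2.0, or 14%.
- Leavers' events kept, time lost: 14.0 / 12.0 = 1.17-fold inflation.
- Events and time both lost: the rate describes completers. There is no bias if leavers have the same rate. If their rate is double, the true average is (12 + 2 × 2) / 14 = 1.143 times the completers' rate, and 1 / 1.143 = 0.875, so the reported rate is 12.5% too low.
- With 18 subjects: 13.5 + 4.5 × 0.5 = 15.75 against 13.5, again 1.17.

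**Sensitivity to exit time (16 entrants).**

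| *m* (years) | 24-month person-years | Seen only on leavers' closing scan | 12-month person-years | Lost without Visit 6 | Inflation if events kept |
|---|---|---|---|---|---|
| 0.25 | 22.75 | 1.75 (8%) | 13.0 | 1.0 (8%) | 1.08 |
| 0.50 | 24.5 | 3.5 (14%) | 14.0 | 2.0 (14%) | 1.17 |
| 0.75 | 26.25 | 5.25 (20%) | 15.0 | 3.0 (20%) | 1.25 |

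**The case against.** A reader might infer that the 12-month rule gives early leavers zero person-time and so always inflates the rate. The documents do not support that. The SAP says the sum runs over all FAS subjects. The Visit 6 substitution can be read as applying to the numerator as well as the denominator, and a withdrawal visit recorded as Visit 6 would supply a date (neither document says whether it is). The person-time is undefined, not zero, and the 1.17 holds only if leavers' events are kept while their time is dropped. A distorted rate ratio needs a further assumption. With 8 per group and leavers split 1 in O-O and 3 in P-O, the ratio would be (7.5 / 7) / (6.5 / 5) = 1.07 / 1.30 = 0.82 with no true difference, but that split is hypothetical.

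The 51% is also an extreme. Capsules are taken morning and evening, drug is finally returned at the Month 24 visit (Protocol 6.3.2), and a scan on the day of the last dose lies inside the window. Nor do the documents place the Month 12 scan after Visit 6: the 7-day tolerance is for the visit itself, and separate timing is given for echocardiography and home collections, not for ultrasound.

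The 14% is itself an upper figure. Subjects who withdraw consent have no further assessments (Protocol 7.4), so their unscanned time yields no ultrasound event under any dating rule.

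Three mitigating points stand in part. Individual ultrasound data are listed and other ultrasound data summarised, so the findings remain visible. Addendum 1 (SAP 11.1) was not available and may hold a visit-assignment rule, although SAP 7.6.2 sets out this calculation without pointing to it. The analysis is descriptive, so no formal test is affected. None of these supplies a defined denominator or restores excluded scans to the reported rate.

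**Conclusion.** The ultrasound point holds on the SAP's own wording. A closing scan dated after the last dose is excluded while its treatment time is kept, which lowers the 24-month ultrasound-based rate. Up to 14% of person-years are affected (8% to 20% over the exit times considered), assuming the planned attrition, a constant rate, and closing scans after the last dose for all leavers. More is affected only if completers' Month 24 scans also post-date the last dose.

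The 12-month point holds as a gap: the window is undefined for about 4 of 16 FAS subjects. Depending on how it is programmed, the rate is correct, inflated 1.17-fold (1.08 to 1.25), or restricted to completers. The gap concerns only the 12-month analysis; at 24 months early leavers contribute time up to their last dose. Both points bear on descriptive estimates of a key secondary endpoint and should be settled before database lock.

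**What to change.** In SAP 7.6.2:

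- **12-month window.** End both person-time and event counting at the earlier of the last dose date and the Visit 6 date. Use day 365 if Visit 6 was missed while dosing continued.
- **Ultrasound events.** Assign findings by visit (Month 12, Month 24 or withdrawal), and count a closing scan done after the last dose as part of that visit. Start person-time at the first open-label dose and end it at the last scan counted. Leave subjects with no follow-up scan out of the ultrasound denominator and report how many there are.

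Person-time should not start at the reference scan. In a seamless transition that scan is the ePHex Week 48 scan (Protocol 6.2), so its use would add time before open-label treatment, which for P-O is placebo time.

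The cost is a few sentences and a small programming change. Two drawbacks should be stated: ultrasound person-time will differ slightly from the adverse-event-based person-time, and stones formed between the Week 48 scan and the first open-label dose cannot be separated from later ones. If Addendum 1 already contains such rules, a cross-reference would be enough.

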2.4 Sample size

Approximately 16 subjects were anticipated to be included in the study, dependent on the number of subjects who complete ePHex and chose to participate in ePHex-OLE. It is anticipated, based on a drop-out rate of 25% per year, that there will be approximately 12 subjects completing the 12-month visit, and 9 subjects completing the 24-month visit.

Assuming a difference between treatment groups in eGFR change at month 24 from baseline of 5 mL/min/1.73 m² with an SD of 3, the power will be greater than 90% with a sample size of 16 subjects. This power calculation is done using a repeated measures model in a two-sided approach with $\alpha=5\%$, a 1:1 allocation ratio for a total of 16 subjects, and assuming a within subject correlation of 0,70.

At the time of signing off the Statistical Analysis Plan it is known that 18 subjects were included.

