If sample size allows it, for comparison between treatments on the total number of kidney stone events, an appropriate model fitting the specific count data will be used, if feasible considering the small sample size. This can be either a Poisson model or a Negative Binomial model, depending on the overdispersion. First a Pearson Chi-squared dispersion statistic is determined. When the dispersion statistic is close to one (i.e. mean is approximately the same as the variance), the Poisson model will be used. If the dispersion statistics however is larger than one (variance >> mean), it is more appropriate to use the Negative Binomial instead. If necessary, depending upon the number of zeros in the underlying data, a zero-inflated model will be used. This analysis is considered the last analysis in the hierarchical approach.

All other US data will be presented in a descriptive summary.

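### The supportive stone-event count model is specified on event totals with no exposure term, although the endpoint is defined as a rate per person-year and follow-up will differ between subjects.

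*SAP*

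**What the plan says.** SAP 7.6.2 (Key secondary endpoints, kidney stone events) gives two kinds of between-group comparison.

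- **Descriptive rates.** Each group's incidence rate is events divided by person-time. Person-time is "calculated as sum of the treatment duration time of all subjects in the FAS"; at subject level the section specifies "where treatment duration is determined based on first and last dose date"; for the 12-month analysis the visit 6 date replaces the last dose date. The incidence rate difference and ratio (IRD, IRR), with 95% CI, are built on these rates (Table 14.2.30). Protocol 12.6.2 also defines the incidence rate per person-year.
- **Count model.** If sample size allows, "for comparison between treatments on the total number of kidney stone events, an appropriate model fitting the specific count data will be used". A second condition in the same sentence repeats that this applies "if feasible considering the small sample size". A Pearson dispersion statistic selects the family: "When the dispersion statistic is close to one (i.e. mean is approximately the same as the variance), the Poisson model will be used". Otherwise the negative binomial is used, and a zero-inflated model is allowed depending on the number of zeros. The result goes to Table 14.2.33, for adverse-event-based and ultrasound-based counts. No offset, exposure variable or log person-time term is named.

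On follow-up, SAP 2.4 states: "It is anticipated, based on a drop-out rate of 25% per year, that there will be approximately 12 subjects completing the 12-month visit", with 9 expected at month 24. It adds: "At the time of signing off the Statistical Analysis Plan it is known that 18 subjects were included".

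**The concern.** The two comparisons use the same events but, as written, estimate different things: one a rate ratio, the other a ratio of event counts. Counts depend on how long each subject was treated, and with 25% drop-out per year that will vary considerably. Two consequences follow.

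1. Any difference in person-time between the O-O and P-O groups, by chance or systematic, passes straight into the model ratio.
2. Variation in follow-up between subjects makes counts look overdispersed even when events are purely Poisson, and the SAP uses dispersion to choose the model.

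At stake is the only model-based comparison planned for this key secondary endpoint. It could disagree with the IRR from the same data solely because one of them ignores exposure.

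**Working it through.** **Inputs.** Drop-out 25% per year and 24 months of treatment (SAP 2.3, 2.4). Stone rates for illustration come from the earlier open-label extension (protocol 4.4.1.4): 0.46 and 0.84 per 48 weeks, that is 0.46 × 52/48 = 0.50 and 0.84 × 52/48 = 0.91 per year. A rate of 2 per year is an assumed upper value. Unequal drop-out by group is also an assumption; the documents give one overall rate. Drop-out is taken as exponential and follow-up T is cut at 2 years.

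**The plan's own figure.** 16 × 0.75 = 12 and 16 × 0.75² = 9 completers, as SAP 2.4 states. The SAP gives no figure for the count model.

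**Step 1: what the model estimates.** With a events in O-O, b in P-O and equal group sizes, a Poisson model with a group term and no offset gives a/b. The SAP's IRR is (a/PT1)/(b/PT2). Hence

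model ratio = IRR × (PT1/PT2).

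The two tables differ by exactly the person-time ratio. With log person-time as offset, the Poisson model returns the IRR itself.

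**Step 2: size of the person-time ratio.** With h = −ln(0.75) = 0.2877:

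- E(T) = (1 − 0.75²)/h = 0.4375/0.2877 = 1.52 years
- Var(T) = 0.44

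*Equal drop-out, 8+8 subjects.* The person-time ratio centres on 1, and its simulated 95% range is 0.63 to 1.58.

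*Assumed 15% versus 35%.* Mean follow-up is (1 − 0.85²)/0.1625 = 1.71 and (1 − 0.65²)/0.4308 = 1.34 years. The ratio is 1.27, so equal true rates appear as about 1.27.

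**Step 3: apparent overdispersion.** For Poisson events at rate L, variance/mean of the counts = 1 + L × Var(T)/E(T) = 1 + 0.289 L.

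| Rate per year | Variance/mean over 24 months |
|---|---|
| 0.50 | 1.14 |
| 0.91 | 1.26 |
| 2 (assumed) | 1.58 |

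This needs no imbalance between groups. In simulation (9+9 subjects, 25% drop-out in both groups, 0.91/year), Pearson dispersion exceeded 1.25 in 44% of trials without the offset and 22% with it. Over the first 12 months the inflation is smaller: 1.04 at 0.50/year and about 1.08 at 0.91/year.

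**Step 4: effect on a Poisson interval.** Simulated coverage of the nominal 95% interval, 8+8 subjects, equal 25% drop-out, true ratio 1, runs with a zero group total omitted:

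| Rate per year | No offset | With offset |
|---|---|---|
| 0.5 | 96% | 97% |
| 0.9 | 93% | 96% |
| 2 (assumed) | 88–89% | 95% |

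Without the offset and with the assumed 15% versus 35% drop-out, coverage is 89% at 0.9/year and 81% at 2/year.

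**Step 5: the SAP's own switch.** Step 4 fits Poisson in every run. When the switch to negative binomial is applied (no offset, equal drop-out, dispersion cut at 1.0 or 1.25), coverage is 97%, 94% and 93% at 0.5, 0.9 and 2 per year. Under 15% versus 35% it is 95–96%, 91% and about 87%. The switch recovers part of the loss by widening the interval. It does not remove the factor in step 1.

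**The case against.** The SAP does not exclude an offset. It asks for an appropriate model and lists no terms at all; person-time is defined just before; and Addendum 1 (programming conventions) is not among the documents. This stands: the exposure term is unspecified, not rejected.

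Several stronger readings are tempting and go too far.

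- *The comparison is biased.* Systematic bias needs mean follow-up to differ between groups. The documents give a single drop-out rate, and all subjects take open-label Oxabact.
- *The dispersion statistic is computed on raw counts.* The SAP calls it a Pearson statistic, which normally comes from a fitted model. Its gloss compares mean with variance, but whether that model carries an offset is open.
- *Overdispersion triggers zero inflation.* The SAP ties zero inflation to the number of zeros. It also describes the negative binomial trigger as a variance well above the mean, and 1.26 is a weak case of that.
- *Without the offset, Poisson would have been adequate.* The earlier study's SDs (0.89 and 1.00) imply variance/mean of 0.89²/0.46 = 1.7 and 1.00²/0.84 = 1.2 on period-adjusted counts. A negative binomial may be needed anyway.

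The analysis also carries little weight. It is conditional on sample size and last in the SAP's order, p-values are only indicative (SAP 7.1), and the person-time IRR is shown beside it. If ePHex is negative and the extension closes early, no statistical analysis is run. These points limit the consequence. They do not supply the missing term in a paragraph that does specify dispersion and zero-inflation rules.

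**Conclusion.** The point holds as a gap in specification with a known, modest effect. As written, the model compares totals for an endpoint that both documents define as a rate, and its ratio carries the group person-time ratio as a multiplier. With equal drop-out the ratio is right on average but picks up a chance factor of about 0.63 to 1.58 in 8+8 subjects. At the earlier study's rates the cost is small: Poisson coverage of about 96% and 93%, and 97% and 94% with the SAP's model switch. A systematic error such as 1.27 arises only under unequal drop-out, which is assumed here. Apparent overdispersion of 1.14 to 1.26 can tip the model choice, and Tables 14.2.30 and 14.2.33 can disagree.

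A reader might infer that the SAP has chosen to ignore exposure, or that the stone-event comparison is unreliable overall. Neither is supported: an offset is not ruled out, and the descriptive IRR already uses person-time. The figures assume exponential drop-out and a constant stone rate common to all subjects.

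**What to change.** In SAP 7.6.2:

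1. State the modelled outcome as the rate of kidney stone events instead of their total number.
2. Include log(t_i) as the offset in the Poisson model, the negative binomial model and the count part of any zero-inflated model. Here t_i is the treatment duration already defined for the incidence rate, cut at visit 6 for the 12-month analysis.
3. Compute the Pearson dispersion statistic from the Poisson model that contains this offset.
4. For ultrasound-based counts, use the time from the second-baseline scan to the last available scan as the exposure. Scans are scheduled only at months 12 and 24 (or done at withdrawal), so days on treatment is not a clean measure of time at risk there. Because the SAP applies the second baseline to former placebo subjects only, say explicitly that the Month 0 scan is meant for both groups.

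The cost is a few SAP sentences, one model option and a derived exposure variable for the ultrasound counts. No new data are needed, and with the offset the Poisson model for adverse-event-based stone events estimates the same quantity as the IRR in Table 14.2.30.
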